Sample size estimation for the efficacy of early versus later physical therapy intervention on patient-reported outcomes (Aim I) was derived from a published study evaluating the effects of early initiation of balance exercises after acute, peripheral vestibular balance disorders as measured by the Dizziness Handicap Inventory (DHI) (Jacobson and Newman 1990, Bamiou, Davies et al. 2000). Patients who presented for treatment within six months of the onset of vertigo had lower DHI scores following physical therapy compared to those who waited longer (22 versus 51, Mann-Whitney, $p=0.007$, Cohen's $d=0.432$). This significant difference in symptomatic outcome based on the effect of physical therapy latency is expected to be at least as profound in the proposed cohort given this study investigates the effects of an even earlier initiation of physical therapy, than the six or more-month latency of the described study. Assuming the effect size between early and late therapy initiation observed in the literature is equivalent in magnitude to the effect size expected in the proposed cohort, a significant effect of time would still be observed at $\alpha=0.05$ with 80% power with a sample size of 36 per group, for both the wearable sensor group and standard physical therapy regimens.

Study design for Aims I and II

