We demonstrated the resolution of symptoms in very mild mTBI was associated with increased head rotation during walking with head turns (Fig. 6). Power analysis for the secondary outcome (head-turn velocity) was derived from our pilot data assessing improved head velocity over time. In an mTBI cohort, a significant rate of change was observed with increasing head-turn velocity over time ($N=26$, $t=4.07$, $p<0.001$, Cohen's $d=0.798$, Fig. 6). With the same sample size of 36 per group, a significant effect of early versus later intervention would still be observable at $\alpha=0.05$ with 80% power, if there is at least a 56% difference in the effect size ($d=0.446$) between the two time-course arms for either intervention group. Similarly, this effect size could also be observed to be statistically significant between the feedback-enhanced intervention and standard exercise regime within either the time to rehabilitation cohorts. Assuming a dropout rate of ~20% over the study period, the expected effects sizes would be found to be significant with a final recruitment of 40 subjects for each of the four groups; totaling 160 people with mTBI for aims I and II combined.

II combined.

Primary outcome: DHI The final sample for Aims I and II will consist of four distinct groups: A) early rehabilitation using wearable sensors at-home, B) early intervention with traditional at home exercise program, C) late rehabilitation using wearable sensors at-home, and D) late intervention with traditional at home exercise program. Linear mixed-effects models will be used in an intention-to-treat design to assess the continuous rate of change in DHI over time in each group. Mixed-effects models will be used to account for within-subject correlation in the repeated measurements across time while addressing any missing data due to dropouts or absentee visits. An on-treatment comparison will also be leveraged, using ordinary least squares to model to bulk change in study outcomes from baseline to study exit for all subjects completing the study.

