To compare the effect of early versus late intervention, the main effect of time (Aim I, comparing groups AB to CD) will be assessed in the mixed-effects model. To compare the effect of rehabilitation with home monitoring versus standard-of-care rehabilitation, the main effect of treatment will be assessed in the mixed-effects model (Aim II, comparing groups AC to BD). To compare whether the effect of at-home monitoring is different between early and late rehabilitation, the interaction between time and treatment will be evaluated using the mixed-effects model. Beyond the main effects of time, treatment and their interaction, individual contrasts among groups will be considered using an ANOVA framework to compliment mixed-effects regression model.

Mixed-effects models will also incorporate covariates found to influence study outcomes, including, but not limited to, age, gender, vestibular function. For the intention-to-treat mixed-effects models, an unstructured error covariance structure will be utilized and parameters will be estimated using restricted maximum likelihood procedures. Missing data points in the analytical sample are considered missing at random and the above approach is sufficient under this assumption. Results will be considered significant at $\alpha=0.05$ with Holm-Bonferroni adjustments to correct for multiple comparisons among the various outcome measures. Model fit and integrity will be examined using a combination of formal fit criteria and visual inspection of residual plots.

Secondary Outcome measures will be assessed using the mixed-effects models as described above to determine the effect of time and treatment on each outcome. To determine the meaningful change of head stability metrics after rehabilitation, the minimal detectable change of our novel outcome measures presented in Table 2 such as attenuation coefficient, cross-covariance of eye, head, and lumbar movements, peak axial rotational velocities, and sequential timing of reorientation will be calculated. Minimally clinically important difference for these novel measures will also be calculated using an anchor-based approach where clinically meaningful difference is based on PGIC.

9. Privacy, Confidentiality, and Data Security

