Statistical Analysis Plan for DOD2: Can Early Initiation of Rehabilitation With Wearable Sensor Technology Improve Outcomes in mTBI?

NCT03479541

April 17, 2024

Statistical Analysis Plan

To evaluate differences in primary and secondary outcomes (all but Patient Global Impression of Change and Dynamic Visual Acuity), we used linear mixed-effect (LME) models with an intention-to-treat design. This statistical approach factors in the 6-week wait as well as the intervention time for the later physical therapy (PT) group, and allowed us to include data from all participants even those who withdrew or were lost to follow-up. Each LME model contained fixed effects for PT onset group (earlier or later PT), time since injury, and the group x time since injury interaction. The interaction effect examined the difference of change in the outcomes over time based on the group. The later PT group served as the reference. Both linear and quadratic time since injury were assessed in the model, and linear time was included in the final model. The full LME models also included apriori covariates of age, gender, and initial SCAT symptom severity total score, and random intercepts to account for within-participant correlations. Outcomes were assessed for normality assumptions in the LME models and were log transformed if necessary. We accounted for participants that withdrew or were lost to follow-up using inverse probability weighting in the model and sensitivity analyses were performed for inverse probability weights.

Primary Outcome

- 1) Dizziness Handicap Inventory (DHI)

Secondary Outcomes:

- 2) Neurobehavioral Symptom Inventory (NSI)
- 3) Quality of Life After Brain Injury (QOLIBRI)
- 4) Return to Activity Question
- 5) Vestibular/Ocular-Motor Screening (VOMS) Tool
- 6) Mini-Balance Evaluation Systems Test (Mini-BESTest)
- 7) Modified Balance Error Scoring System (mBESS)
- 8) Automated Neuropsychological Assessment Metrics (ANAM)
- 9) Instrumented Sway
- 10) Instrumented Walking
- 11) Complex Navigation Task
- 12) Central Sensorimotor Integration (CSMI) Test
- 13) Auditory Processing

Other Pre-specified Outcomes

- 14) Post-concussion Symptom Scale From the Sport Concussion Assessment (SCAT) Tool Version 5
- 15) Insomnia Severity Index (ISI)
- 16) Head Impact Test (HIT) – 6

Statistical Analysis Plan for Patient Global Impression of Change (Secondary Outcome)

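### The stated 80% power at 36 per group does not follow from the stated inputs (44%/46% by two-sided t-test), and 40 per group less 20% dropout leaves 32 completers, not 36

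*Protocol*

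**What the plan says.** The only sample-size justification is in protocol section 8; the SAP has none.

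- **Primary outcome (Sample size calculation for Aims I and II).** The effect comes from a published study of earlier versus later vestibular therapy, reported as "22 versus 51, Mann-Whitney", with Cohen's d = 0.432. Taking that d unchanged, the protocol claims significance at alpha 0.05 "with 80% power with a sample size of 36 per group, for both the wearable sensor group and standard physical therapy regimens".
- **Secondary outcome (Study design for Aims I and II).** The same 36 per group and 80% power are claimed for early versus late on head-turn velocity at d = 0.446, for either intervention group. The protocol adds that "this effect size could also be observed to be statistically significant between the feedback-enhanced intervention and standard exercise regime within either" timing cohort.
- **Dropout (same section).** "Assuming a dropout rate of ~20% over the study period", it says "the expected effects sizes would be found to be significant with a final recruitment of 40 subjects for each of the four groups", 160 in all.
- **Planned analysis (same section).** "Mixed-effects models will be used to account for within-subject correlation in the repeated measurements across time while addressing any missing data" is the stated role of the models. For Aim I, "the main effect of time (Aim I, comparing groups AB to CD) will be assessed in the mixed-effects model". Aim II likewise pools, AC versus BD.
- **SAP.** "Each LME model contained fixed effects for PT onset group (earlier or later PT), time since injury" and their interaction. No sensor term appears.

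**The concern.** An effect near d = 0.43 to 0.45 usually needs about twice 36 per arm for 80% power, so the figure looked wrong on sight. The dropout step looked wrong independently, because going from 40 to 36 allows for a 10% loss, not 20%.

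The text presents four simple comparisons as adequately powered: early versus late within each home-exercise regimen, and sensor versus standard within each timing cohort. A reader who accepts this could take a null sensor result within one cohort as evidence of no effect. The comparison the SAP relies on, early versus late over all participants, is never given a power figure.

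**Working it through.** **Inputs.** From protocol section 8: alpha 0.05; d = 0.432 (DHI) and 0.446 (head-turn velocity); 36 per group; about 20% dropout; 40 recruited in each of four groups. Not stated: the test, its sidedness, and any correlation between repeated measurements. A two-sample t-test is assumed below, both two-sided and one-sided.

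**1. Trying to reproduce the 80%.** Power comes from the noncentral t distribution with noncentrality d × sqrt(n/2) and 2n − 2 degrees of freedom. For d = 0.432 and n = 36:

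- Noncentrality = 0.432 × sqrt(18) = 1.833.
- Two-sided critical value (70 df) = 1.994.
- Power = 44.0%.

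For d = 0.446 the result is 46.3%. A Mann-Whitney test (relative efficiency 0.955) gives 43.3% and 45.6%. The stated 80% is not reproduced.

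**2. Other sample sizes.** Power is shown as d = 0.432 / d = 0.446.

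| Comparison | Two-sided | One-sided | Two-sided detectable d at 80% |
|---|---|---|---|
| 36 v 36 (within stratum, as stated) | 44% / 46% | 57% / 59% | 0.67 |
| 32 v 32 (within stratum, after 20% loss) | 40% / 42% | 53% / 55% | 0.71 |
| 72 v 72 (pooled) | 73% / 76% | 82% / 85% | 0.47 |
| 64 v 64 (pooled, after 20% loss) | 68% / 71% | 78% / 81% | 0.50 |
| 80 v 80 (pooled, no loss) | 77.5% / 80.1% | 86% / 88% | 0.446 |

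**3. Sample size required.** For 80% two-sided power the exact solutions are n = 85.1 (d = 0.432) and 79.9 (d = 0.446), that is 86 and 80 per compared group.

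**4. Crediting baseline adjustment.** With one post-baseline measurement and baseline-outcome correlation r, adjustment inflates the effective d by 1/sqrt(1 − r²). The r needed for 80% is sqrt(1 − (d / detectable d)²):

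- 36 v 36: 0.76 / 0.75.
- 72 v 72: 0.39 / 0.32. For example, sqrt(1 − (0.446/0.4701)²) = 0.32.
- 64 v 64: 0.50 / 0.45. For example, sqrt(1 − (0.432/0.4991)²) = 0.50.

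**5. Crediting repeated measures (illustration only).** Assume two post-therapy visits, the same effect at both, compound symmetry and baseline adjustment. The effective d is then d / sqrt((1 + r)/2 − r²). For d = 0.432 and r from 0.3 to 0.7, two-sided power is:

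- 64 v 64: 90% to 98%.
- 36 v 36: 68% to 85%.
- 32 v 32: 62% to 81%.

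None of these assumptions is in the protocol. The 0.446 is derived from a rate-of-change effect (4.07/sqrt(26) = 0.798; 0.446/0.798 = 56%), so part of the within-subject correlation may already be counted in it.

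**6. Dropout.** 40 × 0.8 = 32 completers per cell, 128 in all. 36/0.8 = 45 per cell, 180 in all. 1 − 36/40 = 10%.

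**7. Source of d = 0.432.** If 22 and 51 are means, d = 0.432 implies an SD of (51 − 22)/0.432 = 67 DHI points. They may be medians, since a Mann-Whitney test is cited, and then this check does not apply.

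**The case against.** The strongest reply is that the protocol plans covariate-adjusted longitudinal mixed models, so an unadjusted single-visit t-test is the wrong yardstick and 44%/46% does not describe the main comparison. Pooling all 160 randomised gives 80 versus 80, where the detectable d is 0.4457, almost exactly the protocol's 0.446. The 80% may therefore be a whole-sample figure attached to the wrong group size. The mixed model also uses partial data from people who leave; if losses accrued evenly, the average number under observation per cell would be (40 + 32)/2 = 36. And the SAP tests a group-by-time slope, for which none of these figures is the power.

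Much of this stands as context. The 44%/46% should not be read as the power of the pooled test, 32 counts completers rather than people contributing data, and the t-test figures are only a guide to the SAP's interaction test.

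It does not rescue the text:

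- The protocol attaches 36 per group to comparisons within each regimen and each cohort, not to the pooled sample.
- The 80 versus 80 case allows no dropout and gives only 77.5% for the primary outcome.
- No correlation, number of visits or one-sided test is stated that would lift 36 versus 36 to 80%.
- The protocol itself offers 40 per group as its allowance for dropout, and it also plans an on-treatment analysis of completers, for which 32 is the relevant count.
- Applying the planned Holm-Bonferroni adjustment could only lower these figures.

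**Conclusion.** The concern holds, and the passage must be corrected.

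- **Power.** On the stated inputs, a between-group t-test at 36 versus 36 falls far short of 80%, whether two-sided or one-sided. More than twice the stated group size would be needed for a two-sided test. The pooled contrasts also fall short when unadjusted, two-sided and allowing for dropout, but they could reach 80% under assumptions the protocol does not state. Their power cannot be judged until the contrast, test, sidedness and correlation are given. This is therefore not a finding that the trial is underpowered.
- **Dropout.** The completer count is wrong whatever test is used.

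The power figures assume a t-test at alpha 0.05 with no multiplicity adjustment, and take 0.432 and 0.446 at face value. The implied-SD check is conditional and the conclusion does not rest on it.

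**What to change.** Keep the enrolment of 160 and the analysis, and revise the sample-size text in protocol section 8:

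1. Correct the dropout line to 32 completers per cell (64 versus 64 pooled), noting that the intention-to-treat mixed model also uses partial data from those who leave.
2. Replace the 80% claim with the contrast, test, sidedness, and any assumed correlation and number of visits.
3. Give unadjusted two-sided detectable effects at 80% power: d about 0.50 for each pooled main effect (64 versus 64) and about 0.71 within one regimen or timing cohort (32 versus 32). A line for 80 versus 80 (d about 0.446, no dropout) would help if that was the source of the figure.
4. Label the within-regimen and within-cohort contrasts exploratory.
5. Confirm how d = 0.432 was obtained from 22 versus 51 before quoting power at that value.

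The cost is rewording only. The unadjusted power statement becomes less favourable.

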Aim II. Home Monitoring: To compare traditional balance rehabilitation versus balance rehabilitation with sensor-based home monitoring of compliance and quality of prescribed exercises. We hypothesize that providing physical therapists with objective measures on compliance and the quality of prescribed exercises performed at home, using wearable sensors, will improve outcomes in rehabilitation. Subjects entering rehabilitation in Aim 1 (both early and late rehabilitation) will be further randomized into either: 1) home exercise program or 2) the same home exercise program with wearable sensors worn on the forehead and trunk to monitor compliance and quality of performance during home exercises. The data from the sensors will be reviewed by the physical therapist at the subsequent weekly visit. All people will be seen 1x/week by a physical therapist and expected to do a home exercise program. People will be tested before and after a 6-week rehabilitation period and again 6 months later to determine long-term retention. In Aim II, we will 1) validate 3D head and trunk motion inertial algorithms with Motion Analyses during the 3 specified exercises 2) develop reports with visual displays for the physical therapist to determine performance and compliance of home

exercises done during each week and 3) compare outcome of the subjects who used wearable sensors during the home exercise program versus those who did not.

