Aim I & II: subjects will be compensated on a graduated scale to encourage retention. The first visit consisting of vestibular and oculomotor tests will be compensated \$40. The second session, consisting of the baseline mobility and further oculomotor tests, will be compensated \$60. The post-therapy mobility and oculomotor session will be compensated \$80, and the retention mobility and oculomotor session will be compensated \$100. Participants will be compensated \$10 dollars per visit for each rehabilitation session. There is a maximum of 5 testing sessions, and approximately eight rehabilitation sessions. Subjects randomized into the standard of care intervention will be tested for mobility and oculomotor at both baseline and prior to starting their physical therapy. Therefore, the standard of care group will have an additional session for which they will be compensated \$60. If a subject does not complete all parts of a session they will be compensated a prorated amount for their time based on the compensation for that session. People who complete all sessions for Aim I & II will be compensated \$275 if they are randomized into the early intervention group, or \$335 if they are randomized into the standard of care group.

Adaptation during COVID- 19 restrictions: Participants will be compensated \$10 for rehab, \$20 for modified Day 1, and \$30 for modified follow up testings. People that complete all modified sessions will be compensated up to \$190.

Home monitoring: Participants will be compensated \$10/per day for approx. 7 days= \$70. This will take place at two different time points during the study for a maximum compensation of \$140.

Aim III: Physical Therapists will be compensated \$100 for their time in training as well as testing. Both people with mTBI and healthy controls will be compensated \$25 for the 60-minute long session

f. Consent Process

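### Aim II (home sensors) has no coherent, undiluted intention-to-treat test: the protocol names a main effect across visits that include unexposed ones, describes the same model as a rate of change, and the SAP has no sensor term

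*Protocol*

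**What the plan says.** Protocol section 2 (Aim II) places the sensor allocation at the start of therapy: "Subjects entering rehabilitation in Aim 1 (both early and late rehabilitation) will be further randomized into either" home exercise alone or the same exercise with sensors. Early groups are tested before therapy, after it and 6 months later. Late groups have one more session. Section 5e states "Subjects randomized into the standard of care intervention will be tested for mobility and oculomotor at both baseline and prior to starting their physical therapy", and section 6 describes the same additional session.

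Section 8 defines groups A to D (early or late, with or without sensors) and says that mixed models will be used "to assess the continuous rate of change in DHI over time in each group". The next paragraph sets the tests. For Aim I it is "the main effect of time (Aim I, comparing groups AB to CD) will be assessed in the mixed-effects model", so the word time here means early versus late, not visit. For Aim II, "the main effect of treatment will be assessed in the mixed-effects model (Aim II, comparing groups AC to BD"). For the question whether the sensor effect differs by timing, "the interaction between time and treatment will be evaluated using the mixed-effects model". No sensor-by-visit term and no post-therapy contrast is named. The error covariance is unstructured. A separate on-treatment analysis is planned, "using ordinary least squares to model to bulk change in study outcomes from baseline to study exit for all subjects completing the study".

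The SAP model for DHI has PT onset group, time since injury, their interaction, three covariates and a random intercept. It has no sensor factor.

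**The concern.** A visit that precedes sensor use cannot show a sensor effect. A treatment main effect in a repeated-measures model averages such visits together with the exposed ones, so it estimates something smaller than the effect of interest. If group-by-time terms are added to obtain a rate of change, the coefficient called the main effect becomes the difference at time zero, before anyone has worn a sensor. If the slope difference is tested instead, the slope in groups C and D includes the wait before therapy.

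Aim II is one of the protocol's three stated objectives. A real sensor benefit could be reported as small or absent because of how the contrast was defined. The timing-by-sensor interaction inherits the problem, because the unexposed share of visits differs between the early and late groups.

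**Working it through.** **The plan's own figures.** The documents give no dilution or power figure for the sensor main effect on DHI, so there is none to reproduce. The only power statement for sensors carries over d = 0.446 from head-turn velocity (56% of a within-group change of 0.798; 0.56 × 0.798 = 0.447). The 36 per group quoted for DHI concerns timing, and is a separate question.

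**Inputs from the protocol.**
- 40 per group and about 20% dropout (section 8): 40 × 0.8 = 32 completers per group.
- Early groups: 3 visits, 2 of them after sensor use. Late groups: 4 visits, 2 of them after sensor use. DHI at the late groups' extra visit is implied by section 6, not stated outright.

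**Assumptions.** DHI scaled to SD 1; a constant sensor effect d = 0.446 at both post-therapy visits; compound symmetry with correlation r from 0.4 to 0.7; timing strata weighted equally; two-sided 0.05. Power = Φ(estimate/SE − 1.96). Each SE below is √{[2v(early)/32 + 2v(late)/32]/4}, where v is the variance of one person's summary.

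**1. Dilution under the all-visit reading.** Share retained = (2/3 + 2/4)/2 = 7/12 = 58%. If DHI is taken at only three visits in every group, it is 2/3 = 67%. With correlation that decays over time, model-based weights give about 61-65%.

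**2. All-visit main effect.** Estimate = 0.583 × 0.446 = 0.26. v(early) = (1 + 2r)/3 and v(late) = (1 + 3r)/4.
- r = 0.4: v = 0.600 and 0.550, SE = 0.134, power 49%.
- r = 0.7: v = 0.800 and 0.775, SE = 0.157, power 38%.

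**3. Group-by-time terms fitted.** Assumed visit weeks: 0, 7, 33 (early) and 0, 7, 13, 39 (late). Generalised least squares gives:
- Treatment coefficient (difference at time zero): 0.11, SE 0.15-0.16, power 10-11%.
- Sensor-by-time slope: 0.0108 SD per week, SE 0.0050 (r = 0.4) to 0.0036 (r = 0.7), power 57-86%.

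**4. Mean of the two post-therapy visits, adjusted for the last pre-therapy DHI.** The estimate stays at 0.446. v = (1 + r)/2 − r² in both strata.
- r = 0.4: v = 0.54, SE = 0.130, power 93%.
- r = 0.7: v = 0.36, SE = 0.106, power 99%.

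Adjusting for both earlier readings in the late groups gives 94-99%.

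**5. Change from baseline to exit (the on-treatment OLS).** The estimate is also 0.446. v = 2(1 − r).
- r = 0.4: SE = 0.194, power 63%.
- r = 0.7: SE = 0.137, power 90%.

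**6. Interaction.** With four late visits, an identical sensor effect in both timing arms appears as 2/3 of its size in the early groups and 1/2 in the late groups. The all-visit interaction is then (2/3 − 1/2) × 0.446 = 0.07 SD when the true interaction is zero.

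**Sensitivity.** At r = 0.5 with 36 per group, the all-visit contrast has 0.32 of the power of the adjusted contrast at d = 0.2, 0.50 at d = 0.446 and 0.94 at d = 0.8. At d = 0.3 and r = 0.8 the ratio is about 0.2.

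**The case against.** The strongest reply is that nothing in section 8 says the sensor effect is averaged over all visits. The sentence introducing the models speaks of rate of change, so the main effects may be shorthand for effects on that rate. This is a fair reading, and under it the 58% does not apply. It does not settle the matter: the two paragraphs still name different quantities, and the late groups' slope still includes the unexposed wait.

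Second, the OLS change analysis is undiluted, and individual group contrasts are also foreseen. That stands, and it means the plan is not without any sound look at sensors. But the OLS analysis is limited to completers and labelled on-treatment, so it cannot serve as the intention-to-treat test. The group contrasts are not tied to any visit.

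Third, the unstructured covariance changes the visit weights. It does: the retained share moves into the low 60s in percent. It does not remove unexposed visits from a main effect.

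Fourth, the numerical inputs are weak. The d of 0.446 is not a DHI effect, and no within-person correlation is given. This is conceded in full.

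A reader might also infer that late-arm participants who withdraw during the wait are lost from the Aim I comparison because they have no sensor assignment. The documents do not settle this. Section 2 suggests allocation at entry to therapy, section 6 describes the randomisation mechanism only for timing, and the plan in section 8 for 40 recruits in each of four groups fits allocation at enrolment. The SAP's Aim I model has no sensor factor, so it would not lose them in any case.

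**Conclusion.** The point holds as a defect of definition with a predictable cost. Read literally, section 8 tests Aim II by a main effect that includes unexposed visits. It also describes the same model as a rate-of-change analysis, and the SAP supplies no sensor contrast to resolve the conflict.

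Under the all-visit reading, the estimate is about 58-67% of the true post-therapy effect. This assumes a constant effect after therapy, equal visit weights and no differential dropout; the lower figure also needs DHI at the late groups' extra visit. With time terms fitted, the named coefficient has almost no power. With a slope test, power is better but below that of the direct contrast in every case computed.

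It is tempting to say that the trial will report 58% of the sensor effect at half the attainable power. The documents do not support that as a flat statement: it is one scenario under one reading, and the power ratio runs from about 0.2 to 0.94 over plausible effect sizes and correlations. Nor do the documents say that Aim II was abandoned; the SAP simply does not mention it.

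**What to change.** In protocol section 8 and in the SAP, define the Aim II estimand as the sensor versus no-sensor difference in DHI at the post-therapy and 6-month visits. Adjust it for the last pre-therapy DHI and timing arm, and analyse everyone randomised to sensor or no sensor as allocated. Define the timing-by-sensor interaction on the same contrast. Keep the OLS change analysis as supportive.

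State when the sensor allocation is made, and confirm that DHI is collected at the late groups' pre-therapy visit. If allocation happens only at entry to therapy, keep the sensor factor out of the Aim I model, as the SAP already does, so that earlier late-arm withdrawals remain in it.

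The SAP is written in the past tense, so it should also say whether any Aim II analysis had been run before this contrast was fixed. The cost is wording in two documents and one additional model, with no new data.
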